6.4.4 Protocol Deviations

All protocol deviations will be listed including classification of importance as agreed prior to database lock.

6.5 Baseline characteristics

6.5.1 Demographics

Descriptive tabulations of demographics at screening will be made. Demographic data (including weight, height and BMI measurements at screening/baseline) will be presented for the FAS and mFAS. Appropriate descriptive statistics for age, height, weight, BMI, race and sex will be given. The listing of demographic data will include information on childbearing potential (for females only).

6.5.2 PH medical history

A descriptive statistics table for PH medical history will be created for the FAS and mFAS, stating the following items: PH type, diagnosis confirmation, time since PH diagnosis (in months) and time on dialysis before screening (in months).

Time since PH diagnosis (in months) will be calculated as the difference in days between first dose date and the date of diagnosis + 1, divided by (365.25/12). Time on dialysis (in months) will be calculated as the difference in days between between first dose date and earliest occurrence of dialysis in the dialysis regimen page + 1, divided by (365.25/12).

For handling missing dates, see section [6.2](#).

6.5.3 Other medical history

Other medical history (including concurrent illnesses and symptoms) will be coded by SOC and PT using MedDRA and presented as number/percentage of patients in each SOC and PT for the FAS and mFAS. SOC and PT will be presented in descending order of frequency. If several SOCs/PTs have the same number of frequencies, the SOCs/PTs will be presented in alphabetical order. These data will also be listed on a per patient level.

In addition, a medical history table will be created containing MH corresponding to the year prior to initial treatment. Identification of relevant medical history terms will be done based on the start date of first exposure to the IMP and the start dates of the medical history events. A cut-off of 365 days prior to the first exposure to the IMP will be used. For handling missing dates, see section [6.2](#).

6.5.4 Other screening data

Pregnancy tests will be listed per visit for females of childbearing potential only and will be combined with the laboratory listings.

6.6 Statistical analysis primary and secondary endpoints

6.6.1 Primary endpoint

The primary endpoint is change in total plasma oxalate level during OC5 treatment, compared to the baseline value. All primary endpoint analyses will be performed for the FAS as primary

analysis, and for the mFAS as post-hoc analysis. All primary endpoint analyses will be done on the overall treatment period, unless otherwise specified.

Summary statistics of the measurements will be presented on a per-visit basis. Both the actual value as well as the change from baseline value will be presented.

Summary statistics tables will also be presented for patients on hemodialysis only and for patients on peritoneal dialysis only separately, if there are more than 3 subjects in any of the groups. In case of less than 3 patients for one of the groups, the separation will not be made, and the summary statistics not presented.

To visualize the effects through time graphically, the following plots will be created:

- Mean +/- SE and individual plots will be created to visualize the course of total plasma oxalate values through time. Both the actual values as well as change from baseline values will be presented. These plots will be created for the overall treatment period as well as the continued treatment period (including the baseline value).
- Combined spaghetti plots will be created using the actual values, for the overall treatment period and the continued treatment period. No spaghetti plots will be created for change from baseline.

Taking into consideration the limited sample size, in addition, a mixed-effect repeated measures model (MRMM) may be performed on the change from baseline values using baseline total plasma oxalate and week as the independent variables. If the assumption of normality is violated, a log transformation will be applied first (and a back transformation will be done on the results). SAS PROC MIXED (with the REML default) will be used for the analysis. The basic SAS code will be as follows.

```
proc mixed data=...;  
  class usubjid;  
  model change= time baseline;  
  repeated time / subject=usubjid type=...;  
run;
```

Considering the variability of plasma oxalate, an unstructured covariance matrix will be used in the model: variances and covariance are allowed to differ at and between measurements. As the use of an unstructured (UN) covariance matrix requires estimation of a larger number of variance and covariance parameters (and is thus computationally more intense and results in a lower power), the model may not converge. If that occurs, the structure will be adapted to respectively AR(1), which assumes that a correlation between two consecutive measurements is higher than between two measurements further apart in time. If convergence is still an issue, then (in order) Toeplitz or Compound Symmetry (CS) will be applied.

The results of this MRMM will be presented in a table including parameter estimates of the regression coefficients, 95% confidence limits and p-values. Although it is understood that multiple patients may drop out and hence a large number of missing data will occur, no sensitivity analysis will be performed, as the sample size is too small to obtain trustworthy results by using a multiple imputation technique. As a consequence, results of the MRMM analysis will be considered only indicative. If too many missing data are causing the model to abort, only descriptive statistics will be displayed.

Furthermore, ordinary least square regressions will be performed for every patient separately using time as independent variable. The individual regression slopes will be averaged and presented in a table using descriptive statistics. Again, because of the number of missing data, results are only to be considered indicative.

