OC3-OL-01 Open-label extension study, non-comparative. 12 to 24 weeks treatment	- 8 sites, n=37 - PH type 1/2 - 16 males, 21 females - Mean age 14, range 6-38	OC3b**: Enteric coated capsule, containing 137 mg (NLT 1E+07 CFU) of lyophilised powder. One capsule was given orally b.i.d. with meals.	- No trends towards reduction in urinary oxalate - No safety concerns - Questionable 24-hour urine collections
OC3-DB-02 Phase II/III, double-blind, placebo-controlled. 24 weeks treatment	- 3 sites, n=34 - PH type 1/2 - 17 males, 17 females - Mean age 22, range 3-62	OC3b buffer**: Buffer formulation, containing 500 mg (NLT 1E+07 CFU) of lyophilised powder. One sachet, reconstituted with water and bicarbonate buffer, given orally b.i.d. before meals.	- No trends towards reduction in urinary oxalate - No safety concerns - Improved 24-hour urine collections

OC5-DB-01 Phase I/II, double-blind, placebo-controlled, multi-centre 8-10 weeks treatment
	
 - 8 sites, n=28 - PH type 1 / 2 / 3 - 15 males, 13 females 
Mean age 14.5, range 3-27
	
OC5#: Enteric coated gelatin capsule, containing 80 mg (NLT 1E+09 CFU) of lyophilised powder.
 
One capsule was given orally b.i.d. with meals.
	
 - No significant difference for primary endpoint (urinary oxalate excretion) - Marked patient heterogeneity with indication that oxalate deposits may be dissolving in OC5-treated patients - Post hoc analyses identified a small, but statistically significant increase of oxalate excretion per creatinine excretion and a statistically significant correlation between change in plasma oxalate and change in Oxalobacter. - No safety concerns

OC5-OL-01 (ongoing) Phase I/II, open-label, non-comparative, multi-centre 6 weeks + up to 36 months.
	
 - 1 site - 6-8 PH patients who are on dialysis 	
OC5#: Enteric coated gelatin capsule, containing 80 mg (NLT 1E+09 CFU) of lyophilised powder.
 
One capsule given orally b.i.d. with meals.
	
 - Study ongoing - Study started in May 2014; 12 patients received study drug, and 1 patient is still ongoing. Interim analysis findings show decreased plasma oxalate and signs of improved myocardial function in patients with low baseline cardiac function.

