5 TRIAL OBJECTIVES AND PURPOSE

5.1 Primary objective

- To evaluate the efficacy of OC5 to reduce total plasma oxalate levels during OC5 treatment in patients with Primary Hyperoxaluria (PH) who are on dialysis.

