6 STATISTICAL ANALYSIS

6.1 General considerations

All evaluations will be explorative in nature, unless stated otherwise. There will be no formal statistical significance testing.

Raw data (in listings) will be presented in the same precision as received. Appropriate rounding will be performed for the summary statistics: arithmetic mean, median, SD (standard deviation) and two-sided 95% confidence limits will be presented with one more decimal than the original data; minimum and maximum values will be presented with the same precision as the original data. In special cases, e.g. after conversion of data, the number of decimals will be determined based on relevance. In frequency tables, percentages will be presented with 1 decimal unless otherwise stated. P-values will be presented with 3 decimals, and those smaller than 0.001 will be replaced by <0.001.

Descriptive statistics presented in summary tables for continuous variables will be the number of non-missing observations (n), arithmetic mean, SD, SE, median, Q1 and Q3, minimum and maximum. All plots will be created using scheduled protocol time or visit on the x-axis. Mean plots will be presenting mean +/- SE. For qualitative data, frequency counts and percentages will be determined. The denominator used when calculating percentages will be the number of subjects in the applicable analysis population.

Baseline is generally defined as the last non-missing and valid measurement/assessment before first dose of study drug. Unscheduled measurements are excluded as baseline value, unless otherwise specified. Change from baseline is calculated as the value at a specific time point minus the value at baseline. For this study, the following definitions are used to define the baseline measurement:

Vital signs: The screening value is used as baseline.

Plasma oxalate: The primary baseline is defined as an average of the available baseline measurements at weeks 2 and 4 (i.e. Visits 2 and 3 respectively). If one baseline measurement is missing for plasma oxalate, the remaining value will be used as baseline value. An additional baseline is the week 10 (Visit 6) assessment of plasma oxalate levels which will serve (only) as a baseline for the assessment of the change in plasma oxalate levels following the 4 week off-treatment period (secondary endpoint). For analyses in the CT phase of the study, a third baseline is defined, being the week 14 value at week 14 of the initial TRT phase.

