6.2 Missing data

No imputation will be performed on missing data, except for those listed below. All analysis will be performed on data available at the visit considered. In summary tables, the number of patients without missing data will be presented (per visit, if applicable), unless otherwise specified. When dates are imputed, a flag will be provided to the CDISC datasets to show this is an imputed rather than an actual date. Listings will only present the actual date, but any calculations can be done on imputed dates.

AE and prior/concomitant medication

Missing/incomplete information related to AEs and concomitant medications will be handled as listed below, when applicable. Following these steps using temporary programming will ensure that missing dates imputations uses the most conservative approach.

- In case of a missing stop date, the stop date will be imputed as follows:
 - In case stop date is partially missing:
 - If the day part is missing, and the month and year present then day will be set to the last day of the month.
 - If both day part and month part are missing, then day and month will be set to 31 December of that year.
 - In case the stop date is completely missing and ongoing is not marked:
 - The event will be assumed to be 'ongoing'.
- In case of a partially missing onset/start date, and stop date is determined to be after first dose date (possibly after imputation), the start date will be imputed as follows:
 - In case start date is partially missing:
 - If the day part is missing, and the month is equal to the month of first dosing date, then day will be set to the date of first dose.
 - If the day part is missing, and the month is not equal to the month of first dosing date, then day will be set to the first day of the available month.
 - If both day part and month part are missing, then day and month will be set to January 1st of the year, unless if year is the same as first dose date year: then the date will be imputed with the first dose date.
 - In case the start date is completely missing:
 - If the stop date is earlier than the first dose date, then the start date will be set to Jan 1st of the stop year. If the stop date is on or after first dose date, then the start date will be set to first dose date.
- In stop date is before first dose date, then start date does not need an imputation, and the event or medication is considered to be prior.

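### The log-transformation fallback in the optional repeated-measures model is written for change from baseline, which has no logarithm when total plasma oxalate falls or stays the same

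*SAP*

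**What the plan says.** The primary objective is directional: "To evaluate the efficacy of OC5 to reduce total plasma oxalate levels during OC5 treatment" (Protocol 5.1). SAP 6.1 defines the outcome by subtraction: "Change from baseline is calculated as the value at a specific time point minus the value at baseline". For plasma oxalate, baseline is the average of the available week 2 and week 4 values.

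SAP 6.6.1 then says that a mixed model "may be performed on the change from baseline values using baseline total plasma oxalate and week as the independent variables". The next sentence is the fallback: "If the assumption of normality is violated, a log transformation will be applied first (and a back transformation will be done on the results". The SAS code beneath it names one response, in the line "model change= time baseline".

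The SAP gives no offset, no ratio-to-baseline outcome, no instruction to log the concentrations before differencing, and no rule for zero or negative changes. It also gives no criterion for judging normality. The model's coefficients, 95% limits and p-values are to be tabulated (Table 14.2.2).

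**The concern.** The two instructions do not fit together. If OC5 works, change from baseline is negative. A logarithm exists only for positive numbers, so the fallback cannot be applied to the records that carry the evidence of benefit. Negative changes are expected, since Protocol 4.4 (Table 3) already reports: "Interim analysis findings show decreased plasma oxalate and signs of improved myocardial function in patients with low baseline cardiac function".

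Nothing later in the plan would catch the loss. SAP 6.2 states: "No imputation will be performed on missing data, except for those listed below", and none of the exceptions covers an undefined logarithm. SAP 6.6.1 rules out a sensitivity analysis for this model and expects a lot of missing data from dropout, so records lost to the transformation could pass for ordinary missingness. They are not ordinary: whether a record is missing depends on its own value, so a likelihood analysis that relies on data missing at random does not correct for it.

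At stake is the only covariate-adjusted model planned for the primary endpoint. Its table could contradict the descriptive table of the same data.

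**Working it through.** **Inputs.** The definition of change, the response variable and the two-value baseline come from SAP 6.1 and 6.6.1. The plan has no figure of its own to reproduce, because SAP 2.4 does not base the sample size on an efficacy assumption. The documents give no SD, CV or effect size, so these are assumed: median 80 µmol/L, between-patient log-SD 0.4, within-patient CV 15–25%, true ratio to baseline r of 1, 0.8 or 0.6.

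**Step 1: worked values, baseline 100.**

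| Visit value | Change | ln(change) | ln(visit/baseline) |
|---|---|---|---|
| 120 | +20 | 3.00 | +0.182 |
| 100 | 0 | undefined | 0 |
| 80 | −20 | undefined | −0.223 |
| 50 | −50 | undefined | −0.693 |

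In SAS the log of a non-positive number returns missing, and PROC MIXED omits records with a missing response. Only the first row would stay in the model. The conversion of total oxalate by a factor of 0.71 (SAP 9.1) scales visit and baseline values alike and leaves every sign unchanged.

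**Step 2: share of records lost.** Let a patient's true level be m, the visit value V = m·r·exp(e) and the baseline B the mean of two values m·exp(e₁) and m·exp(e₂). Each error is normal with variance s² = ln(1 + CV²). A record is lost when V ≤ B. The level m cancels, so the assumed median and between-patient spread do not affect the share lost. To a close approximation ln(V/B) is normal with mean ln r − s²/4 and variance 1.5·s², so

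P(lost) = Φ{(−ln r + s²/4) / (s·√1.5)}.

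For CV 15%: s = 0.149, s·√1.5 = 0.183, s²/4 = 0.0056. For CV 25%: s = 0.246, s·√1.5 = 0.302, s²/4 = 0.0152.

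- No effect (r = 1): 0.0056/0.183 = 0.03, giving 51%; 0.0152/0.302 = 0.05, giving 52%.
- 20% fall (r = 0.8, −ln r = 0.223): 0.229/0.183 = 1.25, giving 89%; 0.238/0.302 = 0.79, giving 79%.
- 40% fall (r = 0.6, −ln r = 0.511): 0.516/0.183 = 2.83, giving 99.8%; 0.526/0.302 = 1.74, giving 96%.

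Simulating 400,000 patient-visits per scenario gives 51–52%, 78–89% and 96–99.8%.

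**Step 3: other assumptions.** With a baseline median of 100, baseline log-SD 0.4, geometric mean ratio 0.7 to 0.9 and log-SD of the visit-to-baseline ratio 0.2 to 0.4, 60% to 96% of records are lost.

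**Step 4: what the fitted model can say.** Every retained change is positive, and exponentiating a fitted mean log-change gives a positive number whatever the data. An exponentiated time coefficient below 1 would mean that the rises get smaller, not that oxalate is below baseline.

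**Step 5: the alternative.** With ln(visit/baseline) no positive concentration is lost. In the same simulation a true ratio of 0.80 comes back as about 0.79 to 0.80. The slight shortfall arises because baseline is an arithmetic mean of two values.

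**The case against.** Four points can be made for the plan.

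- **The word *first*.** It may mean that concentrations are logged before the change is taken, which would be valid. The only explicit log formula in the SAP, for *O. formigenes* counts in 6.6.2, is applied to levels, and the code shown is only the untransformed model. This stands as a possible intention. But the preceding sentence and the code both name change as the response, and nothing tells the programmer otherwise.
- **The model's weight.** It is optional and its results are to be considered only indicative. SAP 6.1 plans no formal significance testing, and Protocol 12.1 rests efficacy on the combined evaluation of individual cases. This stands, and it limits the consequence. It does not excuse the rule: indicative means imprecise, not restricted to one sign.
- **The trigger.** Normality concerns the residuals of change given baseline and week, which need not share any skew in the oxalate levels. How likely the fallback is to be used cannot be judged from the documents.
- **The abort rule.** If missing data stop the model from running, only descriptive statistics are shown. Heavy losses in 6 to 12 patients might trigger that, but a simpler covariance structure might still fit.

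Two stronger readings are tempting. A reader might infer that Table 14.2.2 would report an increase of a few µmol/L, because under the assumed inputs the geometric mean of the retained changes is about +4 to +8 at a true 20% fall. The documents do not support that: the table holds regression coefficients, no adjusted mean is requested, and the simulation did not fit the planned model. A reader might also infer that the primary analysis discards responders. It does not. The loss is by sample, not by patient, about half the samples go even with no drug effect, and the other primary-endpoint displays have no log step.

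**Conclusion.** The point holds for one conditional step of one optional model. As written, the fallback cannot be computed for any sample in which total oxalate fell or was unchanged. If applied literally, it leaves a model fitted only to rises, whose estimates are selected on the outcome and cannot show a reduction. That conclusion is algebraic and needs no assumed figures.

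The size does rest on assumptions: within-patient CV of 15–25%, lognormal error and a two-value baseline give 51–52% of records lost with no effect and 78–89% with a 20% fall. The problem arises only if the model is run, normality is judged violated and the log is taken of the difference. Per-visit summaries, plots and individual regression slopes are unaffected. It should be corrected before the final analysis, but it does not undermine the primary endpoint as a whole.

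**What to change.** Replace the fallback sentence in SAP 6.6.1 with:

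*If normality of the residuals is violated, ln(total plasma oxalate at visit) will be modelled with ln(baseline total plasma oxalate) and week, and results will be reported as the back-transformed ratio to baseline (percent change) with 95% limits. Change-from-baseline differences will not be log-transformed.*

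The code needs the new response and covariate, plus an estimate of the ratio at chosen weeks evaluated at the mean ln(baseline), because the coefficients alone do not give it. If logging the concentrations was always intended, this wording records it.

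The cost is SAP text and one changed response variable, with no new data. The drawback is that the result is a percent change rather than µmol/L, which the descriptive tables still provide.

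### The supplementary mixed model in SAP 6.6.1 cannot run as printed, leaves open whether week is one slope or a set of visit means, and has a covariance plan that does not fit the visit schedule

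*SAP*

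**What the plan says.** For the primary endpoint, SAP 6.6.1 plans per-visit summaries, plots and a separate least-squares regression for each patient. It then says that, "in addition, a mixed-effect repeated measures model (MRMM) may be performed on the change from baseline values". The explanatory variables are the baseline level and week. It does not say whether week is categorical or continuous.

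The code is introduced with "The basic SAS code will be as follows". Apart from blanks for the data set and the covariance type, it consists of:

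- CLASS: "class usubjid"
- MODEL: "model change= time baseline"
- REPEATED: "repeated time / subject=usubjid type"

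On covariance, the section says that "an unstructured covariance matrix will be used in the model". If the model does not converge, the order is AR(1), then Toeplitz, then compound symmetry. AR(1) is justified by correlation being weaker between measurements that lie further apart in time. If missing data make the model abort, only descriptive statistics are shown. The output is coefficients with 95% limits and p-values, planned as Table 14.2.2 (SAP 10.3). The section treats the results as indicative only, and SAP 6.1 rules out formal significance testing.

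**The concern.** Time is the REPEATED effect but is not declared in CLASS, so the code needs a repair before it gives any result. The most obvious repair, adding time to CLASS, also changes what time means in the MODEL statement: a single change per week becomes a separate mean at each visit. Those are different estimates, and the prose does not choose between them.

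The covariance plan is a second difficulty, whichever repair is made. The first structure is far too large for the data. The next two, indexed by visit, treat a 2-week and a 16-week gap as the same step, although the SAP's reason for AR(1) is distance in time.

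At stake is what Table 14.2.2 means. It is the only group-level longitudinal model planned for the primary endpoint.

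**Working it through.** The plan gives no power, alpha or sample-size figure here, so there is nothing to reproduce. SAS was not available. That the code fails rests on the PROC MIXED rule that a REPEATED effect may contain only CLASS variables, not on a run.

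**Inputs**

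- Post-baseline oxalate samples in the first phase: weeks 6, 8, 10, 12 and 14, so 5 (Protocol 6.1; weeks 2 and 4 form the baseline).
- Continued treatment, years 1 and 2: every 4 weeks from week 0 to week 104, so 104/4 + 1 = 27 (Protocol Figure 7 and its notes).
- Year 3: weeks 116, 128, 140 and 156, so 4 (SAP Table 3).
- Visit 9 may coincide with visit 8 (SAP Table 2, note 2).
- 12 patients treated, 8 entering continued treatment (Protocol 11.5.1.2).

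**Visits.** 5 + 27 + 4 = 36, or 35 if visits 8 and 9 coincide.

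**Counts**

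| Quantity | Formula | T = 35 | T = 36 |
|---|---|---|---|
| Mean parameters, time numeric | intercept + slope + baseline | 3 | 3 |
| Mean parameters, time in CLASS | T visit means + baseline | 36 | 37 |
| Unstructured covariance parameters | T(T + 1)/2 | 630 | 666 |
| Most observations, standard schedule | 12 × 5 + 8 × (T − 5) | 300 | 308 |

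Protocol 6.2.5 keeps patients who were already in year 3 on monthly visits. If all eight were, year 3 would have 52/4 = 13 visits. The maximum would then be 60 + 8 × 39 = 372 or 60 + 8 × 40 = 380 observations. The visit set would also grow, to 44 or 45, and the unstructured matrix to 990 or 1,035 parameters. Either way, at most 8 patients inform the covariance among the continued-treatment visits.

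**Gaps.** With 36 visits there are 35 gaps: four of 2 weeks, one unspecified (week 14 to continued-treatment week 0), 26 of 4 weeks, three of 12 weeks and one of 16 weeks. AR(1) or Toeplitz by visit order gives all adjacent pairs the same correlation.

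**Do the repairs differ?** Three were fitted by REML to one simulated data set. Its inputs are assumptions, not from the documents: 12 patients with 8 continuing, SD 20, AR(1) errors with correlation 0.6, and a non-linear mean. Results under AR(1):

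| Repair | Monotone dropout | Plus 20% intermittent missing |
|---|---|---|
| A: time added to CLASS | visit means −8.6 (SE 4.4) at week 10, −15.6 (SE 5.4) at continued week 52 | −9.9 (SE 4.9), −10.8 (SE 6.3) |
| B: class copy in REPEATED, numeric time in MODEL | slope −0.165 per week (SE 0.039); predicts −9.3, −18.5 | slope −0.174; predicts −8.4, −18.2 |
| C: time dropped from REPEATED | identical to B | slope −0.177; predicts −8.3, −18.2 |

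Under compound symmetry, B and C were identical in both cases. The real divide is therefore A against B or C. The gap at continued week 52 (−10.8 against −18.2) comes from one data set with an SE of 6.3 on the visit mean. It shows that the quantities differ, not the size of any bias.

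**The case against.** The case on the other side is substantial.

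- **Status.** The model is optional, additional and indicative, with no formal testing. Protocol 12.1 rests efficacy on the combined evaluation of individual cases. A reader might infer that the primary analysis is broken; the documents do not support that, because the summaries, plots and individual slopes do not use this code. This stands and limits the impact.
- **Template code.** The code is labelled basic and has blanks. An undeclared REPEATED effect gives an error, not a silent bias. This stands too, but a missing CLASS variable, unlike the blanks, leaves the mean model undecided. The descriptive fallback covers aborts due to missing data, not this.
- **The printed code hints at a slope.** Time is numeric in MODEL, and regression coefficients are to be reported. That is a hint, not a statement. Letting variances and covariances differ between measurements needs visit as a class index.
- **Rival repairs.** A reader might infer that every repair gives a different model. Dropping time from REPEATED matches the class-copy fit with sorted complete or monotone data, or under compound symmetry. It differs only with intermittent gaps or unsorted rows under an order-dependent structure.
- **Timing.** A reader might infer that the repair will be chosen in the light of results. The documents do not say when the programs are written. SAP 9.1 does leave unforeseen programming conventions to be settled when they arise, and SAP 7 shows that a first interim analysis has been done, so a written rule is worth having.
- **Unstructured matrix.** The SAP foresees that it may not converge and orders alternatives. That is fair, but the next two structures ignore the unequal gaps. That 26 of 35 gaps are 4 weeks softens this; the 2-week and 12- to 16-week gaps remain.

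**Conclusion.** The point holds for one supplementary, indicative model. As printed, the code does not run, and the SAP leaves open whether it estimates one slope (3 mean parameters) or visit means (36 or 37). The unstructured matrix, with 630 or 666 parameters against at most 300 or 308 scheduled observations from 12 patients, cannot be estimated. The monthly year-3 exception adds observations but also visits, and does not change that. A reader might take 12 × 36 = 432 as the ceiling; it cannot be reached, since only eight patients continued. AR(1) and Toeplitz by visit order do not deliver the dependence on time that the SAP gives as the reason for AR(1).

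This rests on the PROC MIXED syntax rule, the standard visit schedule, and the patient counts in Protocol 11.5.1.2. The simulation only illustrates that the two mean models differ. The consequence is confined to Table 14.2.2, but the correction is worth making before the final analysis.

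**What to change.** In SAP 6.6.1:

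1. State whether week is continuous or categorical, and which estimate Table 14.2.2 reports (slope or visit means).
2. Use a class copy of visit: `class usubjid visitc;` with `repeated visitc / subject=usubjid`. If a slope is wanted, keep numeric `time` and `baseline` in MODEL.
3. Define time as continuous weeks from first dose on one clock across both phases, because continued-treatment weeks restart at 0. Keep one record where visits 8 and 9 coincide, so that no patient has two values at the same time.
4. Replace the unstructured-then-AR(1) sequence with a two-parameter structure on actual weeks, such as `type=sp(pow)(time)`, with compound symmetry as fallback.

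The cost is a few lines of code and a rewritten covariance paragraph; no new data are needed. There is a statistical cost if the slope is chosen. A single line assumes linear change through six weeks on drug, four weeks off drug and up to 36 months of continued treatment. Either state this as a limitation or add a term for the off-treatment weeks.
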